The immediate post-intervention effect of CHAMP (compared to control participants) on each SR outcome variable will be evaluated at post-intervention (month 9). We will examine descriptive statistics for both pre- and post-intervention SR measures of the outcome variables for each group. The change in *cognitive flexibility, working memory, behavioral inhibition, and emotion regulation* scores will be compared between the intervention (CHAMP) and control groups using regression models, adjusting for other confounding factors. Random effects will be included in the model to accommodate for the potential within-cluster correlations due to nested classroom data. We anticipate that some children will have only partial adherence to the intervention (i.e. attend a subset of sessions), thus we will also conduct a dose-response analysis where dose corresponds to number of sessions. We will also investigate the amount of attrition from pre- to post-intervention, and attempt to identify baseline (or pre-intervention) predictors of the likelihood of dropping out (as an indication of possible bias in the change estimates).

Aim 2. Test the hypothesis that improvement in child SR indicators (*cognitive flexibility, working memory, behavioral inhibition, and emotion regulation*) is associated with improved motor competence, perceived motor competence, and objectively-measured PA from pre- to post-test.

We will examine strength of association between each SR variable and our outcomes of interest using bivariate analyses to compare change in SR to change in motor competence, perceived motor competence, and PA (using an alpha value of $p < .05$). We will also use multivariate regression models (controlling for covariates as needed) to examine the association of SR and outcomes in each group (CHAMP and control) in order to test whether the strength of association varies by intervention status.

Sample Size, Power Analysis and Sample Attrition. The sample size was calculated based on our findings from preliminary data. After 9 months, we will be able to detect effects between intervention and control groups with 85% power at an alpha level of 0.05, with a total of 98 subjects (49 subjects per arm). To account for a total of a 16.5% loss at post-intervention, we will recruit 120 subjects (60 subjects per arm) at baseline.

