Specific analysis plan for Aim 2. Examine the associations between SR (cognitive SR, behavioral SR, and emotional SR) and changes in health behaviors (motor competence, perceived competence, physical activity) and health outcomes (body mass index, waist circumference). We will further evaluate the associations between changes in SR and changes in children's health behaviors and outcomes, using regression models. More specifically, we will examine the strength of association between each SR variable and our outcomes of interest using bivariate analyses to compare change in SR to change in motor competence, perceived competence, and PA (using an alpha value of $p < .05$). To test whether the strength of association varies by intervention status, we will use multivariate regression models (controlling for covariates as needed) to examine the association of SR and outcomes in each group (CHAMP and control). Similarly, random effects will be included in the model to accommodate for the potential within-cluster correlations from nested classroom data. We will further apply Structural Equation Models (SEM) to evaluate whether the CHAMP intervention has a causal effect on children's health outcomes mediated through SR.

Data Management. Extreme care to ensure high-quality and secure data will be exercised. All data will be stored securely at the University of Michigan. All data will have only a numerical identifier so that individual respondents, except for video data, cannot be identified. All data will be reported as aggregate statistics and no individuals will be recognizable from the data reported. All data will be scanned for consistency, errors of omission, and appropriateness of the response, and 30% of data will be checked by a blinded member of the research team. Once a coded and cleaned data file has been prepared, frequency distributions and descriptive

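### Self-regulation Aim 2: the only association test with a stated significance level is a bivariate change-on-change analysis with no term for arm or classroom

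*Protocol*

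**What the plan says.** In the Protocol's statistical section for Objective 2, the Aim 2 hypothesis is that improvement in SR "is associated with improved motor competence, perceived motor competence, and objectively-measured PA from pre- to post-test". The analysis offered for it is a set of tests "using bivariate analyses to compare change in SR to change in motor competence, perceived motor competence, and PA", with p < .05 as the stated level. The following sentence adds multivariate regressions "to examine the association of SR and outcomes in each group (CHAMP and control) in order to test whether the strength of association varies" between the arms. No level is given for these. In the Protocol's supplement text, random effects for classroom appear under Aim 1 only.

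The SAP's Aim 2 plan for the supplement has the same structure. It opens with a general reference to regression and at once makes it specific: "health behaviors and outcomes, using regression models. More specifically, we will examine the strength of association between each SR variable". The specific method is again "using bivariate analyses to compare change in SR to change in motor competence, perceived competence, and PA", at p < .05. The within-group regressions have a different purpose: "To test whether the strength of association varies by intervention status, we will use multivariate regression models". After that comes "Similarly, random effects will be included in the model to accommodate for the potential within-cluster correlations from nested classroom data", and then a structural equation model for mediation through SR.

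Both documents also describe an overall multivariable approach for the supplement. The covariates they give as examples are child characteristics (sex, race/ethnicity and, in the SAP, age). Arm is not among them.

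**The concern.** Aim 2 asks whether children whose SR improved more also improved more in motor competence (MC), perceived motor competence (PMC) and PA. Elsewhere the Protocol hypothesises that CHAMP raises SR (Objective 2, Aim 1) and raises MC, PMC and PA (Objective 1, Hypothesis 1). If both are true, CHAMP children sit higher on both change scores. Pooling the arms then produces a correlation even when the two changes are unrelated within each arm, so the test is most misleading when the intervention works as intended.

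Classroom is a second and separate problem. Classes are the unit of randomisation, and the SAP assumes an intra-cluster correlation (ICC) of 0.3 for SR. If the outcome change is also clustered, a test that treats children as independent rejects too often even with no intervention effect.

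The Protocol presents SR as a mechanism of behaviour change. A significant pooled correlation would invite a child-level reading that the test cannot support.

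**Working it through.** **Inputs from the documents**
- Level: 0.05, sidedness not stated, taken as two-sided.
- Sample: 98 evaluable, 49 per arm (Protocol, Objective 2 sample size); 70 CHAMP and 50 control (SAP, supplement power section).
- Classrooms: 10 per arm (Protocol, Objective 2), so 5–6 children per class.
- SR effect: 0.52 SD. This is the SAP's detectable effect, not an expected one.
- SR ICC: 0.3 (SAP), assumed here to hold for the change score.
- PA effect: 12.1/27 = 0.448 SD (Protocol, Objective 1 sample size).
- MC and PMC effects: the Protocol expects them to be larger than for PA but gives no figure.

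**The plan's own figures.** 98/(1 − 0.165) = 117.4, consistent with the 120 recruited. For the SAP's 70/50 split, 0.52/√(1/70 + 1/50) = 2.81, and 2.81 − 1.96 = 0.85 gives about 80% power, as stated, with children treated as independent. Neither figure concerns Aim 2. No power is stated for the association test.

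**Step 1: correlation induced by pooling.** With no within-arm link and a proportion p in CHAMP (q = 1 − p),

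r = d1·d2·pq / √[(1 + d1²pq)(1 + d2²pq)].

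- 49/49: 0.52 × 0.448 × 0.25 = 0.0582; √(1.0676 × 1.0502) = 1.059; r = 0.055.
- 70/50: pq = 0.243; 0.0566/1.057; r = 0.054.

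**Step 2: rejection rates from arm alone.** Simulation, 40,000 replicates, independent children, no within-arm link, SR effect 0.52 SD:

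| Outcome effect (SD) | Source | Bivariate, 49/49 | Bivariate, 70/50 |
|---|---|---|---|
| 0.448 | Protocol, PA | 8.4% | 8.7% |
| 0.6 | assumed | 10.7% | 12.0% |
| 0.8 | assumed | 14.7% | 17.2% |
| 1.0 | assumed | 19.8% | 22.3% |

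With arm in the model the rate is 4.9–5.1%. Within CHAMP alone or control alone it is 4.8–5.2%.

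**Step 3: rejection rates from classrooms alone.** Both intervention effects zero, 20 classes of 5 or 6, SR ICC 0.3, independent class effects, 40,000 replicates:

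| Outcome ICC (assumed) | Classes of 5 | Classes of 6 |
|---|---|---|
| 0 | 5.1% | 4.9% |
| 0.1 | 6.5% | 7.1% |
| 0.3 | 9.0% | 10.0% |

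There is no inflation unless both change scores are clustered.

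**Step 4: both sources together.** With the PA figures, the bivariate test rejects in 9–10%, 10–12% and 14–16% of trials at assumed outcome ICCs of 0, 0.1 and 0.3. At ICC 0.3 in both changes, adding arm without classroom still leaves 9–10%. Arm plus a REML classroom random intercept gives 5.4–5.9% (5,000 replicates, outcome effects 0.448 and 1.0 SD), slightly above nominal.

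**Step 5: power of the within-group regressions.** At an assumed common within-arm r of 0.25 and independent children, power in one arm is 41–42% (n = 49), 43% (n = 50) or 56% (n = 70). The arm-adjusted model in all children has 70% (49/49) or 79% (70/50).

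**The case against.** The strongest reply is that an arm-free analysis is already planned. The within-group regressions cannot be confounded by arm, in the SAP they carry classroom effects, and a pooled result driven only by arm would sit beside weak slopes within each arm. That limits the harm. But both documents assign those regressions to whether the association differs by arm and give no criterion for the association itself. Each also uses only part of a small sample.

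Second, the stated overall approach to associations is multivariable, and 0.05 is the level wherever one is given, so the position of one parenthesis may carry little intent. This is fair as to intent: neither document says that the bivariate result alone decides Aim 2. Still, the general text does not name arm, and the aim-specific text is what an analyst would follow.

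Third, the SAP's random-effects sentence could be stretched to the bivariate step, since a one-predictor model can hold a classroom intercept. That is possible for the SAP but has no counterpart in the Protocol's Aim 2 text, and no reading supplies an arm term.

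Fourth, the hypothesis does not say within arm. When CHAMP moves both variables the pooled correlation is truly non-zero, so 8–9% is not strictly a false-positive rate for the hypothesis as worded. Adjusting for arm also removes association produced through the intervention. This stands, and it is why the risk is one of interpretation. The planned mediation model is the place for the pathway through the intervention.

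Finally, the larger percentages rest on assumed effects and ICCs. That is correct; the documents' own figures support only the PA result.

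**Conclusion.** The concern holds. In both documents the p < .05 criterion in Aim 2 is attached only to a bivariate change-on-change analysis that, as it reads, has no arm or classroom term.

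On the documents' figures the size for PA is small: an induced correlation of about 0.05 and rejection in 8–9% of trials instead of 5%, using a detectable SR effect and independent children. It could reach 11–22% for MC and PMC, but only under assumed effects of 0.6–1.0 SD. Clustering alone adds nothing if the outcome change is unclustered and brings the rate to 9–10% at an assumed outcome ICC of 0.3.

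The aim is secondary, it belongs to a supplement that cohort 2 does not join, and the primary conclusion is untouched. The change should be made because it is inexpensive and prevents a predictable misreading.

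**What to change.** Name one analysis as the test of each Aim 2 association: a mixed model of outcome change on SR change, arm and the prespecified covariates, with a classroom random intercept, fitted to all children. Attach the 0.05 level to the SR-change coefficient. Keep the pooled bivariate correlations and the arm-specific slopes as description, without a decision attached. Use the same wording in the Protocol and the SAP.

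As a minor clarification, judge whether the association varies by intervention status from the SR change × arm estimate and its confidence interval, in a second model labelled exploratory.

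The cost is SAP and Protocol wording and one further model for each association; no new data are needed. The low power of the interaction should be stated. For correlations of 0.3 in one arm and 0 in the other, the Fisher z difference is 0.310. At 49/49 the standard error is √(1/46 + 1/46) = 0.209 and power is about 32%. At 70/50 it is √(1/67 + 1/47) = 0.190 and power is about 37%.

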Fig 7: Power to detect changes in MC and PMC.

Objective 2 (CHAMP effect on Self-Regulation)

Data Analysis Plan. Data analyses for this SOBC supplement will follow the funded Parent Award R01HL132979-01 strategy. We will transform skewed outcome variables as needed, run descriptive statistics, apply transformations to assure normality, and assess potential covariates to include. While maximum effort will be made to retain all subjects and minimize the amount of missing data, we anticipate there will be some data lost-to-follow-up and incomplete measures. Thus as is our practice we will address missing data by applying advanced statistical techniques, such as “multiple imputations” using PROC MI in SAS and IVEWARE SAS macro. Our overall approach is to employ multivariate analysis using a general linear modeling approach to assess associations among key variables using the appropriate models based on the distribution of the data (i.e., normal, categorical data, count data, reaction time data) and including covariates as warranted (gathered in Parent Award; e.g., child sex, race/ethnicity).

Data analyses for this SOBC supplement will follow the funded Parent Award R01HL132979-01 strategy. We will transform skewed outcome variables as needed, run descriptive statistics, apply transformations to assure normality, and assess potential covariates to include. While maximum effort will be made to retain all subjects and minimize the amount of missing data, we anticipate there will be some data lost-to-follow-up and incomplete measures. Thus as is our practice we will address missing data by applying advanced statistical techniques, such as “multiple imputations” using PROC MI in SAS and IVEWARE SAS macro. Our overall approach is to employ multivariate analysis using a general linear modeling approach to assess associations among key variables using the appropriate models based on the distribution of the data (i.e., normal, categorical data, count data, reaction time data) and including covariates as warranted (gathered in Parent Award; e.g., child sex, race/ethnicity).

Aim 1. Test the hypothesis that CHAMP improves child SR indicators (*cognitive flexibility, working memory, behavioral inhibition, and emotion regulation*) from pre- to post-test, compared to control.

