Overall Analysis Plans. We will apply transformations to assure normality, run descriptive statistics, and assess potential covariates to include. While maximum effort will be made to retain all participants and minimize the amount of missing data, we anticipate there will be some data lost-to-follow-up and incomplete measures. Therefore, we will address missing data in the analysis plan by applying advanced statistical techniques, such as “multiple imputations” using PROC MI in SAS and IVEWARE SAS macro. Our overall approach will be to employ multivariate analysis to assess associations among key variables using the appropriate models based on the distribution of the data (i.e., normal, categorical data, count data, reaction time data). Since this is a cluster-randomized trial, adjusting the covariates (e.g., child sex, age, race/ethnicity) will aid in controlling additional unbalancesess due to the limited sample size. All analysis will be done using SAS 9.3 or R 4.1.0⁹⁶⁻⁹⁸. Additionally, we will perform “intent to treat”

analysis and assume all subjects comply to the assigned group. Findings/results from the study will also follow the CONSORT guidelines.

Power considerations. When we calculate the sample size and power, we assumed the intra-cluster correlation is 0.3. The achievable power is calculated for a detectable effect size, which is the detectable mean difference standardized by the square root of sample variance. Given the randomization design with 70 children in the intervention group and 50 children in the control group, we have 80% power to detect a difference in cognitive SR, behavioral SR, or emotional SR with an effect size of 0.52 and a Type I error level of 0.05.

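### Supplement Aim 2 asks whether the association between self-regulation (SR) and outcomes differs by arm, but names only regressions within each arm and no test of the difference between slopes

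*Protocol*

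**What the plan says.** **Protocol, section E, Objective 2, Aim 2.** After bivariate analyses of change against change, multivariable regression is used for this step: "examine the association of SR and outcomes in each group (CHAMP and control) in order to test whether the strength of association varies" between arms.

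**SAP, Specific analysis plan for Aim 2.** The purpose comes first: "To test whether the strength of association varies by intervention status, we will use multivariate regression models (controlling for covariates as needed"). The method follows: "to examine the association of SR and outcomes in each group (CHAMP and control"). The SAP adds that "random effects will be included in the model to accommodate for the potential within-cluster correlations from nested classroom data", and that an SEM will examine whether CHAMP acts on health outcomes through SR.

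**Decision criterion.** The only one in these paragraphs is p < .05. It belongs to the earlier step, where the text reads "using bivariate analyses to compare change in SR to change in motor competence, perceived motor competence, and PA (using an alpha value of", and not to the by-arm models.

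**Covariates.** The protocol speaks of "including covariates as warranted (gathered in Parent Award; e.g., child sex, race/ethnicity"). The SAP says "adjusting the covariates (e.g., child sex, age, race/ethnicity) will aid in controlling" residual imbalance.

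**Link to the parent project.** The protocol's Objective 2 analysis plan opens with "Data analyses for this SOBC supplement will follow the funded Parent Award R01HL132979-01 strategy". The parent Aim 2 analysis, in both documents, includes exploratory interaction tests.

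**The concern.** Whether an association varies by arm is a question about the difference between two slopes. It needs an estimate of that difference with a standard error. Separate regressions yield a slope and a p-value for each arm. An analyst could carry out the stated step exactly and still have no test of the question posed.

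The gap leaves room for an informal answer in which one arm's slope is significant, the other's is not, and the arms are declared different. That is not a test of a difference. With the SAP's unequal arms (70 and 50), it would also tend to single out CHAMP, because the larger arm reaches significance more often when the true association is the same in both.

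**Working it through.** The documents give no power, error rate or sample size for comparing slopes, so there is no stated figure to reproduce. The power statements in the supplement concern differences in SR between arms.

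**1. Is a contrast named anywhere?**
- Supplement Aim 2, both documents: regression in each group. There is no product term, coefficient contrast or decision rule.
- Parent Aim 2, both documents: intervention by time, baseline measures by time, and a general exploratory line on intervention effects modified by behaviour change. None names SR.
- SEM (SAP): mediation of the CHAMP effect through SR. This is a different quantity from a difference in SR-outcome slopes between arms.

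**2. How many tests?**
- Protocol: 4 SR indicators × 3 outcomes = 12.
- SAP: 3 SR domains or 5 components, with 3 outcomes (bivariate sentence) or 5 (adding BMI and waist circumference). This gives 3 × 3 = 9 up to 5 × 5 = 25.
- Chance of at least one false positive, if independent and each at 5%: 1 − 0.95^9 = 37%; 1 − 0.95^12 = 46%; 1 − 0.95^25 = 72%.

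**3. Power of a direct comparison, correlations 0.3 against 0.** Arm sizes are 70/50 (SAP, Power considerations) and 49/49 (protocol, Objective 2 sample size). The correlations are assumed; the documents give none.
- SE of the Fisher-z difference = √(1/(n1−3) + 1/(n2−3)): √(1/67 + 1/47) = 0.190; √(2/46) = 0.209.
- 95% CI half-width = 1.96 × SE: 0.373 and 0.409.
- atanh(0.3) = 0.3095. Power ≈ Φ(0.3095/SE − 1.96): 37% and 32%, ignoring clustering.
- Simulated with 10 classes per arm and ICC 0.3 in both SR change and outcome residual: 31% and 26% from within-class slopes only; about 36% and 31% with a random intercept and known ICC. The SAP assumes 0.3 for its SR power; applying it to the outcomes is an added assumption. With an outcome-residual ICC of 0.05 to 0.1, the random-intercept figures are 34 to 35% and 29 to 30%.

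**4. Error rate of the interaction test.** Simulated, random intercept, known ICC 0.3.
- Same slope in every class and equal residual variance: about 5%.
- Equal mean slope of 0.25 in both arms, but slopes varying between classes: about 8% at an assumed SD of 0.2 (7 to 9% over arm splits and repeated simulations) and about 12% at an SD of 0.3 (10 to 12%).
- Residual SD assumed 1.5 times larger in control (70/50): 7%.

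**5. Illustration only: comparing arms by which one reaches p < 0.05.** The documents do not state this practice. Assume the same true r in both arms and ignore clustering. Per-arm power p = P(|N(atanh(r)·√(n−3), 1)| > 1.96), and P(exactly one significant) = p1(1−p2) + p2(1−p1). At r = 0.25 with 70/50: 0.552 × 0.583 + 0.417 × 0.448 = 0.51.

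| Assumed common r | 70/50 | 49/49 |
|---|---|---|
| 0 | 10% | 10% |
| 0.1 | 21% | 19% |
| 0.2 | 45% | 40% |
| 0.25 | 51% | 48% |
| 0.3 | 47% | 49% |
| 0.4 | 22% | 30% |
| 0.5 | 4% | 7% |

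**The case against.** **The plan declares a test.** Both documents give testing for variation by arm as the purpose of these models, and a product term, or a contrast of the two fitted slopes, would satisfy the wording. No model in either document is written out term by term, the primary one included. This stands as far as it goes: the gap is incomplete specification, not a choice of an invalid method. But the one operational phrase given is regression in each group, and that does not reach the stated purpose.

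**The parent strategy may cover it.** The supplement defers to that strategy, and an intervention effect modified by behaviour change is, algebraically, the same product term. But that line sits under the parent's long-term aim and does not mention SR, so coverage has to be inferred.

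**A reader might infer that the team plans to compare the arms by significance, or that about half of such comparisons would be false.** The documents support neither. They never state that practice, and the rates near 50% also need an assumed correlation of about 0.25 to 0.3. At 0.1 or 0.4 the rate is 19 to 30%, and at 0.5 it is 4 to 7%.

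**The interaction test is not a guarantee either.** It keeps its 5% level only under the conditions in step 4 of the working, and its power is low.

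**Conclusion.** The concern holds as a minor gap in specification. Supplement Aim 2 poses a between-arm question and states a within-arm method; nothing else in the documents supplies the missing contrast.

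That conclusion rests on the text and on no assumed number. The sizes are illustrative. The false-difference range of about 4 to 51% depends on an unstated practice and an assumed common correlation between 0 and 0.5. The power range of about 26 to 37% depends on assumed correlations of 0.3 and 0 and, for its lower end, on the assumed ICC.

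The reach is small. This is one sub-question of a secondary aim, in a study that the protocol's Clinical Trial Statement calls exploratory, and Cohort 2 does not take part in Objective 2. The primary MVPA analysis and the SEM mediation analysis are unaffected.

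**What to change.** Replace the by-group sentence in both documents with the following.

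- For each SR-outcome pair, fit one mixed model of outcome change on arm, SR change, arm × SR change and the plan's covariates (e.g. age, sex, race/ethnicity), with a classroom random intercept.
- Take the interaction estimate and its 95% CI as the test of whether the association varies by arm. Report the arm-specific slopes, with CIs, from the same model.
- As a sensitivity check, allow the SR slope to vary between classes or use cluster-robust standard errors.
- Label the tests exploratory, fix the SR and outcome lists, state the resulting number of tests, and say whether and how multiplicity is handled.

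The cost is one model term, one sensitivity analysis and a few sentences. No new data are needed, and the bivariate analyses and SEM stay as planned. The drawback is low power: with about 100 to 120 children a null interaction settles little, so interpretation should rest on the CI and not on the p-value.
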